2.2 Randomization

Allocation of patients is done when all inclusion and exclusion criteria are satisfied. Patients are randomly assigned in a ratio of 1:1 to one of two treatment arms:

- 1) Transitional care (intervention) or
- 2) Usual care (control).

Allocation of patients is done with the data management system (REDCapTM) that also hosts the electronic case report forms (eCRFs). Allocation is stratified by:

- Discharge site (Hôpital Fribourgeois, Centre hospitalier Bienne, CHUV Lausanne, Hôpital neuchâtelois)
- Readmission risk category according to the simplified HOSPITAL score (intermediate vs high risk, i.e. a HOSPITAL score of 4 or 5 vs ≥ 6)

The readmission risk category is documented on eCRF “Eligibility” by variable `strat_1`, the discharge site is coded via the patient ID. The random allocation is performed centrally within the data management system using permuted block with random block sizes of 2, 4 and 6. Investigators receive the allocation only after the eCRF “Eligibility” has been completed. The allocation is documented by variable `alloc_a_group` on eCRF “Eligibility”.

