4.3 Adherence and protocol deviations

Major protocol deviations are

- Violation of inclusion or exclusion criteria
- No informed consent signed
- Crossing-over to the other treatment arm
- Patients not discharged home or to nursing home
- Patients not discharged alive
- Change of HOSPITAL score risk group between inclusion and patient discharge
- Not receiving post-discharge component of the intervention and at least one of the follow-up phone calls (unless the patient was readmitted or died before the follow-up phone call).
- Blindness breach

These protocol deviations will be summarized by treatment group using absolute and relative frequencies.

Table 2: Derivation of protocol deviations.

Protocol deviation	eCRF sheet	Variable	Variable type	Derivation
Violation of inclusion or exclusion criteria				
Adult patient	Baseline Characteristics	patient_age	Continuous: years	patient_age<18
Planned discharge home or nursing home	Eligibility	discharged_alive_home	Binary: No, Yes	discharged_alive_home==No
Patient expected to be discharged alive?	Eligibility	discharged	Binary: No, Yes	discharged==No

CTU Bern	SAP for TARGET-READ phase 2	05.03.2019
	Version 1.0	Page 10 27

Protocol deviation	eCRF sheet	Variable	Variable type	Derivation
Hospital stay of at least 24 hours	Baseline Characteristics	computed_nbdays	Continuous: days	computed_nbdays>=1
Patient at higher risk of 30-day readmission (HOSPITAL score ≥ 4)	Eligibility	hosp_score_simple	Integer: 0-12	hosp_score_simple<4 or hospital_change==Yes & hosp_score_simple_2<4
Patient at higher risk of 30-day readmission (HOSPITAL score ≥ 4)	Baseline Characteristics	hospital_change	Binay: No, Yes	
Patient at higher risk of 30-day readmission (HOSPITAL score ≥ 4)	Baseline Characteristics	hosp_score_simple_2	Integer: 0-12	
Previous enrolment into the current study	Eligibility	already_enrolled	Binay: No, Yes	already_enrolled==Yes
Not living in the country in the next 30 days	Eligibility	home_ch	Binay: No, Yes	home_ch== No
No phone to be reached at.	Eligibility	phone	Binay: No, Yes	phone== No
Not speaking French or German (depending on the site)	Eligibility	lang	Binay: No, Yes	lang== No
Informed consent	Eligibility	consent_signed	Binay: No, Yes	consent_signed==no

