Crossing-over to the other treatment arm	Protocol Violation	category_interv_notdone category_interv_1funotdone category_interv_2funotdone category_interv_crossover	Binay: No, Yes	(category_interv_notdone==Yes & category_interv_1funotdone==Yes & category_interv_2funotdone==Yes) or category_interv_crossover==Yes
Not discharged home or nursing home	Baseline Characteristics	discharged_destination	Categorical: Home, Nursing home, Other acute care Hospital, Acute geriatric, Rehab, Palliative care, Other, Unknown	discharged_destination!=Home & discharged_destination!=Nursing home
Not discharged alive	Baseline Characteristics	discharged_alive	Binay: No, Yes	discharged_alive==No
Change of HOSPITAL score risk group between inclusion and patient discharge	Eligibility	hosp_score_simple	Integer: 0-12	hospital_change==Yes & hosp_score_simple==4 or 5 & hosp_score_simple_2 > 6
Change of HOSPITAL score risk group between inclusion and patient discharge	Baseline Characteristics	hospital_change	Binay: No, Yes	
Change of HOSPITAL score risk group between inclusion and patient discharge	Baseline Characteristics	hosp_score_simple_2	Integer: 0-12	or hospital_change==Yes & hosp_score_simple>6 & hosp_score_simple_2==4 or 5
Not receiving post-discharge component of the intervention and at least one of the follow-up phone calls	Protocol Violation	category_interv_notdone	Binay: No, Yes	category_interv_notdone==Yes or (reach_phone_d3==No & reach_phoned_14==No)
Follow-up calls	Follow-up calls	reach_phone_d3, reach_phone_d14	Binary: No, Yes	
Blindness breach	Protocol Violation	description	Free text	Includes "blind"

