4.4.2 Per-protocol set (PPS)

The PPS consists of all subjects in the FAS who received the allocated treatment and did not have any major protocol deviations (section 4.3).

5 Trial Population

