6.3.4 Subgroup analyses

The primary outcome will be analyzed for subgroups defined by the stratification factors for randomization:

- Risk for readmission (HOSPITAL score of 4 or 5 vs ≥6)
- Clinical site
- Diabetes
- Chronic heart failure
- COPD
- Cancer

CTU Bern	SAP for TARGET-READ phase 2	05.03.2019
	Version 1.0	Page 22 27

- Living place (nursing home vs rest)
- Living status (alone vs rest)
- Health insurance (Semi-private and private vs rest)

Table 9: Derivation of subgroups

Subgroup	eCRF sheet	Variable	Categorization
HOSPITAL score	Eligibility	hosp_score_simple	if hospital_change==no: hosp_score_simple > 5
	Baseline Characteristics	hosp_change	else:
		hosp_score_simple_2	hosp_score_simple_2 > 5
Clinical site	-	record_id	substr(record_id,1,3)
Diabetes	Index Diagnosis	comorbidities__5	comorbidities__5==checked
Chronic heart failure	Index Diagnosis	main_dx_at	main_dx_at==Heart failure or
		comorbidities__9	comorbidities__9==checked
COPD	Index Diagnosis	main_dx_at	main_dx_at==COPD exacerbation or
		comorbidities__7	comorbidities__7==checked
Cancer	Index Diagnosis	main_dx_at	main_dx_at==Neoplasm or
		comorbidities__8	comorbidities__8==checked
Living place	living_type	Categorical: Home, Protected apartment, Nursing home, Other, Unknown	living_type==Nursing home
Living status	living_st	Categorical: With spouse/partner, With another person, Alone, Unknown	living_st==Alone
Health insurance	insur	Categorical: Base, Base+compl, Semi-private, Private, Other, No insurance	insur==Semi-private or insur==Private

Subgroups will be analyzed using regression models with the treatment group, the subgroup and their interaction and the stratification factors used at randomization as covariates. If possible, a binomial model with identity link function will be used and the effects will be reported as risk differences with 95% CIs. Otherwise, a Poisson model with identity link and robust standard errors (leading to risk differences) or a binomial model with logit link (leading to odds ratios) will be considered. Models with and without interaction will be compared using a likelihood ratio test and the p-value will be reported as p-value for interaction. Results will be presented in a forest plot.

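### Table 2 codes the 24-hour stay rule backwards and sets the high-risk cut one point too high, so the per-protocol set cannot be built as written

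*SAP*

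**What the plan says.** Section 4.3 lists the major protocol deviations, and Table 2 turns each into a rule on eCRF variables. In the eligibility rows the rule describes the failing state. The adult-age row is "patient_age<18", and the rows for telephone, language, consent, earlier enrolment and expected discharge work the same way. The row labelled "Hospital stay of at least 24 hours" has the rule "computed_nbdays>=1".

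For a change of risk group between inclusion and discharge, Table 2 gives two conditions. The upward one is "hospital_change==Yes & hosp_score_simple==4 or 5 & hosp_score_simple_2 > 6". The downward one, also conditional on a documented change, is "hosp_score_simple>6 & hosp_score_simple_2==4 or 5".

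Elsewhere the boundary is placed differently. Section 2.2 stratifies randomization by "a HOSPITAL score of 4 or 5 vs ≥ 6". Table 9 in section 6.3.4 codes the high-risk subgroup, where the score changed, as "hosp_score_simple_2 > 5". The objectives in section 1.2 and Table 10 in section 7 also start the high-risk group at 6.

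Section 4.4.2 defines the per-protocol set (PPS) as patients of the full analysis set (FAS) who received the allocated treatment and "did not have any major protocol deviations". Section 6.3.2 repeats the analysis of all outcomes in the PPS, and section 6.7 has a second statistician reproduce the primary outcome in both sets.

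**The concern.** The stay rule has the wrong direction: a patient who meets the criterion is flagged as a major deviator, and one who fails it is not. The risk-change rule has the wrong cut. Its intermediate group is 4 or 5 and its high-risk group starts at 7, so a score of 6 belongs to neither group, although the randomization puts it in the high-risk stratum.

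The two errors pull in opposite directions. The first removes nearly everyone from the PPS. The second keeps patients whom section 4.3 says to exclude. Both distort the table of deviations by arm, and through the PPS definition they reach every per-protocol result and the per-protocol half of the replication.

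**Working it through.** **Denominator.** The SAP's 1,380 serves only as a base for counts, but it can be reproduced. Inputs from sections 2.3 and 4.2: control rate 0.27; relative reduction 25%, so the intervention rate is 0.27 × 0.75 = 0.2025; two-sided 5% level; 80% power; 10% loss. With the normal-approximation formula for two proportions without continuity correction,

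n = [1.960 × √(2 × 0.23625 × 0.76375) + 0.842 × √(0.27 × 0.73 + 0.2025 × 0.7975)]² / 0.0675² ≈ 621 per arm.

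Allowing for loss, 621 / 0.90 = 690 per arm, or 1,380 in all. This agrees with the SAP.

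**Stay rule.** The rule as written, and its negation, applied to some recorded stays:

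| `computed_nbdays` | Criterion met | Flagged as written | Flagged with `<1` |
|---|---|---|---|
| 0 | no | no | yes |
| 0.5 | no | no | yes |
| 1 | yes | yes | no |
| 2 | yes | yes | no |
| 10 | yes | yes | no |

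The flag is the exact complement of what is needed. The PPS can hold only patients with a recorded stay below one day. The SAP does not say how many there would be, so the share is an assumption:

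| Assumed share with stay under 1 day | Largest possible PPS, of 1,380 |
|---|---|
| 0% | 0 |
| 1% | 14 |
| 2% | 28 |
| 5% | 69 |

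These are upper limits, since other deviations would remove further patients.

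**Risk-change rule.** Read the 4-or-5 part as it is plainly meant, that is, the score is 4 or the score is 5. Table 2 gives the score range as 0 to 12.

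- True groups: intermediate {4, 5} has 2 values; high {6, …, 12} has 7. Ordered moves between them: 2 × 7 × 2 directions = 28.
- Flagged as written: high is {7, …, 12}, 6 values. 2 × 6 × 2 = 24.
- Missed: 28 − 24 = 4, namely 4→6, 5→6, 6→4 and 6→5.
- Wrongly flagged: none.
- With the cut at 6 or more: 28 of 28.

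Section 2.3 describes the score as out of 13. With 13 as the maximum the counts become 28 of 32 flagged, and the same four moves are missed. These are counts of score pairs, not of patients. The SAP gives no distribution of scores or of changes, so the number of patients affected cannot be derived. The missed moves do include both one-point crossings of the boundary, 5→6 and 6→5.

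**The case against.** The strongest reply is that this is a slip in a secondary part of the plan that would correct itself. The primary analysis uses all randomized patients by allocation. Neither the stratification variable nor the subgroup coding in Table 9 relies on Table 2. An almost empty PPS could not go unnoticed, and the row label makes the intention clear. Table 2 is also shorthand rather than executable code, as the 4-or-5 expressions show, so a programmer must interpret it anyway.

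Much of this stands. The FAS result, its type I error and its power are untouched, and the inverted stay rule would probably be caught. The argument does not cover the cut above 6. That rule yields a plausible PPS and a plausible deviation count, and a second statistician who codes from the same table would reproduce the error. Nor is correction during analysis harmless: sections 2.8 and 7 leave the statistician unblinded, so an analyst who knows the allocation would be redefining a prespecified population.

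Two smaller reservations are fair. A fall from 6 to below 4 is not missed, because the separate eligibility row on the minimum score catches it; only the four moves listed escape. And Table 4 describes `computed_nbdays` only as length of stay in days. If it is a difference of calendar dates, which the SAP does not settle, a limit of one day would let an overnight stay shorter than 24 hours pass. That concerns how closely the variable captures the criterion, not the direction of the rule.

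**Conclusion.** Both rules are wrong as written, by the SAP's own definitions. Taken literally, the stay rule removes from the PPS every patient who meets the criterion in recorded days, leaving at most 0 to 69 of 1,380 if 0% to 5% have shorter stays. The risk-change rule misses 4 of 28 moves between the risk groups, which are all those with 6 as the high-risk score. Its effect on the PPS appears once the stay rule is corrected; its effect on the deviation table is immediate. The conclusion on the risk-change rule rests on reading the 4-or-5 expressions as intended; the share of short stays affects only the illustrated PPS sizes. The damage is confined to the deviation table, the per-protocol analyses of all outcomes and the per-protocol replication.

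**What to change.** Amend two derivation entries in Table 2 before database lock.

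1. Stay: `computed_nbdays<1`. State in the same row whether the variable is elapsed time or a difference of calendar dates.
2. Change of risk group: `hospital_change==Yes & ((hosp_score_simple in {4,5} & hosp_score_simple_2>=6) or (hosp_score_simple>=6 & hosp_score_simple_2 in {4,5}))`. The brackets and set notation also remove the ambiguity of the present expressions.

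The cost is a short SAP amendment. No data collection, sample size or primary analysis changes, and the boundary at 6 is the one already used for stratification and subgroups.

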5.6 Procedural characteristics

Procedural characteristic include the components of the transitional care intervention and are collected for the transition care group only. The pre-discharge component of the intervention is documented at baseline (visit 1) on eCRF “Pre-discharge component”, the follow-up phone calls (visit 2 and visit 3) on eCRFs “Follow-up call 1 (Day 3)” and “Follow-up call 2 (Day 14)”. Evaluations of the procedural characteristics will be based on the FAS. They will be presented in a descriptive summary table—continuous variables as mean and standard deviation or median and quartiles and categorical variables as absolute and relative frequencies.

Table 6: Procedural characteristics: pre-discharge components.

Description	Variable	Type
Basic information about her/his main diseases has been performed?	pat_info	Binary: No, Yes
Which information about those comorbidities have been given to the patient?		
Heart failure	inf_shee_giv_1	Binary: Unchecked, Checked
Coronary disease	inf_shee_giv_2	Binary: Unchecked, Checked
Peripheral artery disease	inf_shee_giv_3	Binary: Unchecked, Checked
Atrial fibrillation	inf_shee_giv_4	Binary: Unchecked, Checked
Chronic obstructive lung disease	inf_shee_giv_5	Binary: Unchecked, Checked
Stroke	inf_shee_giv_6	Binary: Unchecked, Checked
Gastrointestinal bleeding	inf_shee_giv_7	Binary: Unchecked, Checked
Chronic renal failure	inf_shee_giv_8	Binary: Unchecked, Checked
Liver cirrhosis	inf_shee_giv_9	Binary: Unchecked, Checked
Thromboembolism	inf_shee_giv_12	Binary: Unchecked, Checked
Diabetes	inf_shee_giv_13	Binary: Unchecked, Checked
Other*	inf_shee_giv_88	Binary: Unchecked, Checked
No listed comorbidity	inf_shee_giv_0	Binary: Unchecked, Checked
Medication reconciliation has been performed and explanation about medication list?	med_reco	Binary: No, Yes
Have you noticed any medication discrepancy that needed to be transmitted to the medical team?	med_reco_disc	Binary: No, Yes
Patient education about general health recommendation has been performed?	pat_educ	Binary: No, Yes
Dependence Level: score of the Katz Index	katz_ind	Integer: 0-6
Post discharge follow-up visit to the treating physician has been planned?*	folup_plan	Binary: No, Yes
Discharge summary sent to the treating physician	dis_sumpcp	Binary: No, Yes
Barriers to a safe discharge, including patient's ability to carry out the discharge plan has been assessed	finalcheck	Binary: No, Yes

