*Further specifications are given as free text and will be listed only.

Table 7: Procedural characteristics: follow-up call 1 (Day 3) and follow-up call 2 (Day 14).

Description	Variable	Type
Patient reached by phone	reach_phone_d3 or reach_phone_d14†	Binary: No, Yes
Reason why the patient wasn't reached*	reas_pat_notre_d3 or reas_pat_notre_d14†	Categorical: Death, No answer, Other
Death source of information*	death_sourceinfo_d3 or death_sourceinfo_d14†	Categorical: Next of kin, Treating physician, Hospital, Death certificate, Other
Death was due to an accident/trauma?	trauma_death_d3 or trauma_death_d14†	Categorical: No, Yes, Unknown
Cause of death (according to certificate of death if possible)	cause_death_d3 or cause_death_d14†	Free text
Condition improved since discharge	cond_impr_d3 or cond_impr_d14†	Categorical: No, or rather no, Yes or rather yes, Stable, New symptom
Since your discharge of the hospital, do you have more pain?	morepain_d3 or morepain_d14†	Binary: No, Yes
How does the mobility/walking distance change since discharge?	red_wal_dis_d3 or red_wal_dis_d14†	Categorical: Mobility/walking distance improved, Mobility/walking remained about the same, Mobility/walking decreased, Not able to evaluate
Capacity to prepare meals alone?	cap_meal_d3 or cap_meal_d14†	Binary: No, Yes
Weight trend over the last days/weeks	wei_tren_d3 or wei_tren_d14†	Categorical: Increased, Reduced, Stable, Unknown
Glucose values most often†	glu_val_tre_d3 or glu_val_tre_d14†	Categorical: Between 4-10, >10, Between 10-15, >15, Unknown
Do you take your medication as prescribed?	medicasprescribed_d3 or medicasprescribed_d14†	Binary: No, Yes
Is there any medication discrepancy between current list and list of discharge?	med_discr_d3 or med_discr_d14†	Binary: No, Yes
Presence of any of those medications?	pre_med_d3 or pre_med_d14†	Categorical: Anticoagulants, Narcotics and opiates, Sedatives, Insulin
Did any of these Adverse Event occur since discharge?		
Dizziness	adv_dru_ev_d3_1 or adv_dru_ev_d14_1†	Binary: Unchecked, Checked
Bleeding	adv_dru_ev_d3_2 or adv_dru_ev_d14_2†	Binary: Unchecked, Checked
Hypoglycemia	adv_dru_ev_d3_3 or adv_dru_ev_d14_3†	Binary: Unchecked, Checked
Delirium	adv_dru_ev_d3_4 or adv_dru_ev_d14_4†	Binary: Unchecked, Checked
Lethargy / Oversedation	adv_dru_ev_d3_5 or adv_dru_ev_d14_5†	Binary: Unchecked, Checked
Nausea / vomiting	adv_dru_ev_d3_6 or adv_dru_ev_d14_6†	Binary: Unchecked, Checked

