6.3 Analysis methods

6.3.1 Primary analysis

The primary analysis will be based on the FAS. Missing data will be handled according to section 6.4.

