6.3.2 Secondary analyses

All outcomes will also be analyzed in the PPS. Only patients without missing value for the respective outcome will be considered (complete cases).

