6.7 Quality control

A second statistician will reproduce the analysis of the primary outcome (for both the FAS and the PPS) based on the exported data. The risk difference and the 95% confidence interval should not differ by more than 0.01, the p-value by 0.001. Otherwise, the reason for the difference will be determined and a consensus must be reached.

7 Changes from the protocol

The SAP is consistent with principle features of the statistical methods described in the protocol. The following deviations were made:

Table 10: Changes from protocol

Header	Change	Reason
Blinded analysis	Blinded analysis not implemented	The allocation can immediately be seen from the eCRFs because only patients in the intervention group have follow up phone calls. It would therefore need an extra statistician that carefully prepares the data so that it is not possible to see the allocation. Given the open-label nature of the study and the straightforward analysis this additional effort seems not to be justified.
Secondary outcome "Medication adherence: 4-item Morisky Medication Adherence Scale (MMAS-4)".	Removed	High license fees would incur
Secondary endpoint "Number of planned hospital readmissions" and "Total number of planned days of hospitalizations"	Added	Information about the planned readmissions is of interest but was not considered in the protocol.
Test for the analysis of primary and binary secondary outcome	Stratified Cochran-Mantel-Haenszel test instead of simple chi-squared test	Stratification factor should be considered in the analysis
Subgroup HOSPITAL score	Categories 4 or 5 vs ≥ 6 instead of 5 or 6 vs ≥ 7	Categories correspond to stratification of the randomization
Subgroup clinical site	Added	Used as stratification factor in randomization
Subgroups cancer, living place, living status and health insurance	Added	Of interest, not mentioned in protocol

References

¹ Clinical trial protocol: Transition care intervention targeted to high-risk patients to reduce readmission (TARGET-READ): A randomized controlled trial, Version 1.1, 13.02.2018

² SOP Data preparation and programming, CS_STA_SOP_05, version 02, 15.08.2015

³ SOP Statistical data validation, CS_STA_SOP_02, version 02, 15.08.2015

⁴ Klingenberg, B. 2014. A new and improved confidence interval for the Mantel–Haenszel risk difference. *Statistics in medicine*, 33(17): 2968.

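### Table 2 leaves out the section 4.3 exception for patients readmitted or dead before the calls, so the coded rule can drop early-event patients from the PPS in the intervention arm only

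*SAP*

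**What the plan says.** Section 4.3 counts failure to receive the intervention component and the follow-up calls as a major deviation, with an exception: "unless the patient was readmitted or died before the follow-up phone call".

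Table 2 turns this into a derivation: "category_interv_notdone==Yes or (reach_phone_d3==No & reach_phoned_14==No" (closing bracket follows). Neither the row's label nor its derivation repeats the exception. Its only variables are `category_interv_notdone` and the two reach-by-phone fields; it uses no death or readmission variable.

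The consequences are set elsewhere:

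- Section 4.4.2: the PPS keeps subjects of the full analysis set (FAS) "who received the allocated treatment and did not have any major protocol deviations (section 4.3".
- Section 6.3.2: "All outcomes will also be analyzed in the PPS".
- Section 6.3.1: "The primary analysis will be based on the FAS".
- Section 5.6: the procedural data, which include the call forms, are "collected for the transition care group only". Table 10 in section 7 confirms that "only patients in the intervention group have follow up phone calls".
- Table 7: the reason for not being reached is coded "Categorical: Death, No answer, Other", for both the day-3 and the day-14 call.

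**The concern.** The text and the derivation of the same deviation disagree, and no other section restores the exception. A programmer would code Table 2.

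The omission works in one arm. A control patient has no call form, so the call term can never be met there. In the intervention arm it can be met because the patient had died or was back in hospital. Deaths and unplanned readmissions are primary events, so membership of the PPS then depends on the outcome in one arm, which is what the exception in 4.3 prevents.

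Two further effects follow. Deviations are tabulated by group, so early deaths and readmissions could be reported as non-adherence. Section 6.7 also asks a second statistician to reproduce the primary outcome in the PPS. If one codes from the text and the other from Table 2, they may build different sets; if both use Table 2, the check will not find the error.

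**Working it through.** **Can the route occur?** Table 7 offers death as a reason for not being reached, so the form expects a death to be recorded with the reach field at No. A patient who does not answer at day 3 and dies before day 14 can have No on both forms. So can a patient who is in hospital at both calls.

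**Inputs from section 2.3.** Expected 30-day risk 27%, relative reduction 25% (giving 20.25%), 80% power, 10% loss, 690 per arm; two-sided 5% from section 4.2. These are consistent: the pooled-variance formula for 27% against 20.25% gives 621 per arm, and 621/0.90 = 690, the plan's figure. The SAP gives no number for patients affected by the Table 2 row, so what follows is illustration. It assumes 27% in both arms (no true effect) and 690 per arm. Differences are transitional care minus usual care, so negative values favour the intervention.

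**Early-event patients removed from the intervention arm.** Expected events: 0.27 × 690 = 186.3.

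- One event removed: (186.3 − 1)/689 − 0.27 = −0.106 points.
- A share x of the arm removed, all primary events (assumed): (0.27 − x)/(1 − x) − 0.27.
  - x = 1% (about 7 patients): 0.26/0.99 − 0.27 = −0.74 points.
  - x = 2% (about 14 patients): 0.25/0.98 − 0.27 = −1.49 points.

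**Unreached patients who are event-free to day 14.** The same row removes these, as 4.3 intends. With a constant hazard (assumed), their risk over the remaining 16 days is 1 − 0.73^(16/30) = 0.1545.

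- 3% of the arm removed this way (assumed): (0.27 − 0.1545 × 0.03)/0.97 − 0.27 = +0.36 points.
- 1% early events together with that 3%: (0.27 − 0.01 − 0.1545 × 0.03)/0.96 − 0.27 = −0.40 points.
- Event-free removals that offset one removed early event: 0.73/(0.27 − 0.1545) = 6.3.

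**Scale.** The 95% CI half-width at 690 per arm is 1.96 × √(2 × 0.27 × 0.73/690) = 4.68 points. A smaller PPS would make it wider.

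**The case against.** The strongest reply is that the reach is limited. The primary analysis uses the FAS, and section 4.4.2 points to section 4.3, whose text does state the exception. The intended rule is therefore on paper and only its coded form is incomplete. This is correct, and it keeps the point at the level of a correction that should be made.

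The path is also narrow. The call term needs an explicit No at both calls. A patient reached at day 3 who has an event later is not caught, and one readmitted early may be reached at day 14. Table 8 accepts a death from any one form, so the day-14 form may be blank after an early death, and a blank does not satisfy `==No`. All of this stands. If early deaths leave the form blank and blank is not read as No, they add nothing.

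The net direction is open, because unreached event-free patients push the other way. That stands for the row as a whole. It does not excuse the omission: 4.3 intends those removals, whereas the missing exception adds only patients it meant to keep. The size of the offset is itself uncertain. The PPS analysis is complete-case (section 6.3.2), so unreached patients who also lack the day-30 outcome would be out anyway.

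Finally, section 4.4.2 separately requires receipt of the allocated treatment. Read strictly, that clause could remove the same patients even after Table 2 is corrected. This is a fair point, and the correction has to settle it.

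Staff could apply the exception by hand when completing `category_interv_notdone`, but this does not help, because the call term is joined to it by an `or`.

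**Conclusion.** The point holds. Table 2 does not carry out the rule stated in section 4.3, and followed as written it can remove early-event patients from the PPS in the intervention arm alone. Taken by itself, removing primary events in this way moves the PPS primary result towards the intervention, by about 0.11 points per event. The 1% and 2% cases are assumptions, and both results are well inside the half-width. The number affected cannot be read from the SAP and may be small, and the net PPS shift is not determined. The text-against-derivation mismatch is certain and needs no assumption. The FAS primary analysis does not change.

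**What to change.** Make the Table 2 cell match section 4.3 by judging each call separately. A call counts as missed only if its reach field is No and no death or readmission occurred between index discharge and that call, using `reas_pat_notre_d3`/`reas_pat_notre_d14`, the death dates and `unplanned_in_1`. Flag the deviation if `category_interv_notdone==Yes` or both calls count as missed. A patient who does not answer at day 3, is readmitted on day 8 and is missed at day 14 is then not flagged.

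State also:

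1. the reference date for a missed call: the call date, which section 3.2 implies is held, or the end of the Table 1 window;
2. whether planned readmissions count and, if so, which date variable is used, since Table 8 lists only their number and total days;
3. how a blank day-14 form is treated;
4. whether patients excused under 4.3 satisfy the treatment-received condition in 4.4.2.

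Smaller corrections that do not carry the finding: `reach_phoned_14` should read `reach_phone_d14`; the first-readmission date is `unplanned_in_1` in Table 8 but `unplanned_1_in` in section 6.3.3; and the post-discharge component named in 4.3 and Table 2 should be reconciled with the pre-discharge component in 5.6.

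The cost is one derivation cell and a few sentences before database lock. Not-reached reasons, death dates and the first unplanned-readmission date are already collected. A planned-readmission date would have to be identified only if planned readmissions are to count.

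### Table 2 does not code the minimum-exposure rule of section 4.3: blank call sheets, the call-not-done flags and the exemption for early death or readmission are left out of the per-protocol derivation

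*SAP*

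**What the plan says.** Section 4.3 lists as a major deviation: "Not receiving post-discharge component of the intervention and at least one of the follow-up phone calls (unless the patient was readmitted or died before the". The sentence closes with the call itself, so patients readmitted or dead before it are exempt. Section 4.4.2 removes anyone with a major deviation from the per-protocol set, and section 6.3.2 analyses all outcomes in that set.

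The Table 2 row label repeats the rule without the exemption: "Not receiving post-discharge component of the intervention and at least one of the follow-up phone calls". Its derivation is "category_interv_notdone==Yes or (reach_phone_d3==No & reach_phoned_14==No", closing bracket omitted here. The variable list of the same row, and Table 7, spell the day-14 variable `reach_phone_d14`.

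The flags for a first or second call not done appear only in the cross-over row: "category_interv_notdone==Yes & category_interv_1funotdone==Yes & category_interv_2funotdone==Yes) or category_interv_crossover==Yes".

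Section 5.6 describes the parts of the intervention. "The pre-discharge component of the intervention is documented at baseline (visit 1) on eCRF “Pre-discharge component"; the follow-up calls are documented at visits 2 and 3. These data "are collected for the transition care group only". Table 10 confirms that only intervention patients have the calls.

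**The concern.** The per-protocol analysis is meant to estimate the effect in patients who were treated as planned. That requires a rule for minimum exposure that is the same in text and code and that gives one answer for every pattern of data. Three things stand in the way:

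- The component named in the rule does not exist as a separate item in section 5.6.
- The call condition gives no instruction for a blank field and does not use the variables that record a call not done.
- An exemption stated in the text is absent from the code.

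The second and third faults push in opposite directions. Keeping patients who had no call pulls the per-protocol estimate towards no effect, if the calls work. Dropping patients because they died or were readmitted before a call removes primary-outcome events from one arm only, which favours the intervention. The statistician is not blinded (section 2.8, Table 10), so these choices should not be left open until the analysis.

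**Working it through.** The plan states no figure on this point, so the check is mainly one of logic.

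**1. Component.** Section 5.6 has the pre-discharge component, call 1 and call 2. After discharge there are only the calls. Read literally, section 4.3 names the calls twice and the pre-discharge component never. In Table 2, `category_interv_notdone` stands apart from the two call flags, which suggests that it records the pre-discharge part. The steps below assume so.

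**2. Complete data.** With Yes or No in all three fields there are 2 × 2 × 2 = 8 patterns. The code flags the 4 with `category_interv_notdone` = Yes and the 1 with that field No and both calls No. The other 3 have the pre-discharge part and at least one call. Leaving the exemption aside, the code therefore matches the evident intent when nothing is blank.

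**3. Blanks.** Take an intervention patient with `category_interv_notdone` = No and both call-not-done flags = Yes, so that no call was received:

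| reach_phone_d3 | reach_phone_d14 | Minimum-exposure row | Cross-over row |
|---|---|---|---|
| No | No | flagged | not flagged |
| No | blank | not flagged | not flagged |
| blank | No | not flagged | not flagged |
| blank | blank | not flagged | not flagged |

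The cross-over row never catches this patient, because it also needs `category_interv_notdone` = Yes. Three of the four patterns pass both rows.

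**4. Arm.** The row has no arm restriction, and the call fields are blank throughout usual care. If blank counted as No, every usual-care patient would be flagged. If blank does not count as No, the three patterns in step 3 pass. The row as written works in both arms only on the second reading.

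**5. Exemption.** Table 7 gives Death as a reason for not being reached, and Table 8 counts that entry as a primary-outcome event. A patient with No at both calls and Death as the reason is therefore an event under Table 8, exempt under section 4.3, and a deviator under Table 2. The same conflict arises for a patient readmitted before the calls and entered as No at both. Usual care has no call sheets, so this row removes nobody there.

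**6. Scale per patient.** The number of patients is unknown, but the design rates show what one patient does. From section 2.3: 27% in usual care and 0.75 × 27% = 20.25% under the intervention. These rates reproduce the plan's sample size:

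- n per arm = [1.960 × √(2 × 0.23625 × 0.76375) + 0.8416 × √(0.27 × 0.73 + 0.2025 × 0.7975)]² / 0.0675² = 621 after rounding up
- 621 / 0.90 = 690 per arm, 1,380 in total

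Taking the full arm of 690 as the largest possible per-protocol arm:

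- one patient without calls wrongly kept, assumed to carry the full usual-care risk: (0.27 − 0.2025) / 690 = 0.0001, about 0.01 percentage points towards no effect
- one patient with an event wrongly dropped: (1 − 0.2025) / 689 = 0.0012, about 0.12 percentage points in favour of the intervention

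Per patient, the missing exemption weighs roughly 12 times as much (0.001157 / 0.000098). This says nothing about how many patients of either kind there will be.

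**The case against.** The strongest reply is that little may go wrong in practice.

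- A call that was never made can be entered as No with reason Other, and No at both calls is caught. The SAP does not say that such sheets are left blank. This stands: the leak is a possibility, not a certainty.
- Section 3.2 plans a completeness check of the section 5.6 variables before database lock, and the call fields are among them. This also stands, but a check does not say how a blank that remains is to be classified.
- An analyst could sensibly apply the row to the intervention arm only and count blanks as not received. That is a good reading, but the SAP does not state it. Section 6.7 has a second statistician reproduce the per-protocol primary result, and the two could read the row differently.
- Section 4.4.2 also requires that the allocated treatment was received. No derivation is given, so this is partial cover.
- The component name and the misspelt variable are slips that the code and the row's own variable list largely settle. Agreed; they need correcting but would seldom change who is selected.

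A reader might infer more than the document supports: that untreated patients will certainly be counted as adherent, that a given share of the arm is misclassified, or that the primary result is at risk. The first depends on eCRF completion, which is not described. The second has no basis in the SAP. The third is wrong, because the primary analysis uses all randomized patients as assigned (sections 4.4.1 and 6.3.1).

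**Conclusion.** The point holds as a mismatch between rule and derivation. The component name in section 4.3 and Table 2 does not fit section 5.6. Intervention patients without any call can remain in the per-protocol set when at least one call field is blank and the other is not Yes. Patients whom the text exempts are dropped when both fields are No. The last two errors work in opposite directions, so even the sign of the net effect is unknown.

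The conclusion assumes that `category_interv_notdone` records the pre-discharge part and that the code is applied as printed. Only the secondary per-protocol analyses are affected. The full analysis set and the sample size are not. No total size can be derived; the per-patient shifts of about 0.01 and 0.12 percentage points rest on the design rates and a full arm of 690. This should be corrected, but it does not endanger the main conclusion of the trial.

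**What to change.** Before database lock, amend section 4.3 and the Table 2 row:

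- Reconcile the component name with section 5.6, so that text, row label and code refer to the same thing.
- Apply the row to the intervention arm only.
- Derive no call received as (`category_interv_1funotdone`==Yes or `reach_phone_d3`!=Yes) and (`category_interv_2funotdone`==Yes or `reach_phone_d14`!=Yes).
- Exclude from that condition patients whose recorded death or unplanned readmission precedes the call, in line with the exemption already in section 4.3. Without this step, counting blanks as not received would drop still more events from the intervention arm.
- Correct `reach_phoned_14` to `reach_phone_d14`.

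Three details need a line each. A call that was not made has no date, so the SAP should name the reference date; Table 1 gives visit windows. Section 4.3 says readmitted without qualification, whereas Table 8 lists readmission dates only for unplanned stays, so the SAP should confirm that these are meant. The first readmission date is `unplanned_in_1` in Table 8 but `unplanned_1_in` in section 6.3.3, and the eCRF name should be used.

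The cost is a wording change and one derivation line, using fields already on the eCRF. The per-protocol set may change slightly in size.
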